# Table 3:Hazard ratios detectable in the CIPHER study for a range of assumptions,
based on a cohort of 4,000 participants.

Ratio of presence:	Squared correlation	Incidence of	Hazard ratio	o detectable
absence of covariate	with other covariates	PSH	90% power	80% power
1:1	0 (i.e. unadjusted)	40%	1.18	1.15
	0.3		1.21	1.18
	0.5		1.26	1.22
	0 (i.e. unadjusted)	30%	1.21	1.18
	0.3		1.25	1.21
	0.5	1.30		1.26
1:2	0 (i.e. unadjusted)	40%	1.19	1.16
	0.3		1.23	1.19
	0.5		1.28	1.23
	0 (i.e. unadjusted)	30%	1.22	1.19
	0.3		1.27	1.23
	0.5		1.32	1.27
1:5	0 (i.e. unadjusted)	40%	1.24	1.21
	0.3		1.30	1.25
	0.5		1.36	1.30
	0 (i.e. unadjusted)	30%	1.29	1.24
	0.3	1.35		1.30
	0.5	1.43		1.36
1:10	0 (i.e. unadjusted)	40%	1.33	1.28
	0.3		1.40	1.34
	0.5		1.49	1.41
	0 (i.e. unadjusted)	30%	1.39	1.33
	0.3		1.48	1.40
	0.5	1.59		1.49
1:20	0 (i.e. unadjusted)	40%	1.46	1.39
	0.3		1.58	1.48
	0.5		1.71	1.59
	0 (i.e. unadjusted)	30% 1.55		1.46
	0.3		1.69	1.57
	0.5		1.86	1.71

#### 4.8 Measures taken to avoid bias

Measures taken to protect against bias are described below in relation to the bias domains potentially affecting non-randomized studies of interventions [40]:

#### i. Bias due to confounding

Two extremes of practice are possible:

- (a) surgeons prefer some variants in surgical technique to others and apply their preferred variant to all of their patients, irrespective of the patients' characteristics;
- (b) surgeons use several variants in surgical technique and choose the variant for a particular patient according to the patients' characteristics or other factors.

In situation (a), we expect that the risk of bias due to confounding will not be a serious issue since all surgeons are likely to operate on a wide variety of patients, i.e. predictors *other than* variations in the way a surgeon creates a stoma will be distributed similar within all surgeons; if (a) can be shown, there is also the possibility of adjusting for potential predictors other than surgical variations using an instrumental variable, i.e. surgeon preference one or other surgical method [41]. In situation (b), the risk of bias due to confounding will be potentially serious and we are likely to have to control for confounding by conventional, multivariable methods since an instrumental variable is unlikely to be available. We will be able to distinguish between situations (a) and (b) on the basis of the surgical data accruing as the study progresses.

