Both patient and surgical factors may influence the risk of developing PSH. Patient factors include advanced age, obesity, wound infection, malignancy, inflammatory bowel disease, immunosuppression and a raised intra-abdominal pressure [5-7]. Surgical risk factors are less well defined. Risks are considered to relate to the methods of stoma formation. There are multiple techniques used in practice with no overall standard approach. For example, location and size of the abdominal wall defect created during stoma formation is thought to vary between surgeons [6]. Some surgeons use mesh around a stoma to help prevent PSH, whilst others do not [8]. Additional factors that may influence PSH formation are whether the surgery was planned or unplanned [6] and the seniority of the surgeon performing the procedure. Part 1 of Phase A of the CIPHER study will investigate variations in surgical methods and identify key surgical steps that may influence PSH formation. This will involve reviewing the current literature and producing descriptive case studies of stoma formation in the operating theatre. These steps will thus define the surgical variables of interest for measurement in the cohort study (Phase B).

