#### 5.7 Selection of confounders

The challenges of confounding have been described above (see 0). We will be able to inspect the accruing data to find out how participating surgeons choose particular surgical variants in relation to participants' characteristics. Assuming that analyses will need to take confounding into account by one method or another, we will consider the list of confounding factors in **Table 5**.

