#### 8. Statistical analyses

#### 8.1 Plan of analysis

The data will be analysed according to the intention to implement a surgical step and will be reported in accordance with the principles of the CONSORT guidelines (but not items relating to randomization). A detailed statistical analysis plan will be prepared prior to locking the database. The primary outcome, time to PSH (defined as the time when PSH confirmed by imaging) and secondary time-to-event outcomes, will be analysed using survival methods. The models will take account of the hierarchical structure of the data; i.e. participants, nested within surgeons nested within centres. The hazards of key predictors will be estimated, with 95% confidence intervals, after adjusting for important procedure, patient and surgeon confounding factors.

Exploratory analyses will be used to inform the choice of survival distribution (e.g. Weibull). The factors included in the model, the modelling strategy and the approach to handling correlated covariates will be documented in the statistical analysis plan. Participants free from a PSH at final follow-up will be censored. Follow-up will also be censored if bowel continuity is restored, if participants have a redo stoma or die. These circumstances leading to censoring may be informative and sensitivity analyses (setting survival times to the longest observed times) will be undertaken to assess the potential impact of informative censoring. Secondary continuous outcomes will be analysed using a mixed regression models, again taking account of the hierarchical structure of the data and the repeated measurements over time. Binary outcomes (e.g. complications) will be analysed using

logistic regression. If the frequency of the outcomes allows, these models will also take account of the hierarchical structure of the data.

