#### 13.2 Data handling, storage and sharing

#### 13.2.1 Data handling

Data will be entered onto a purposed designed database. Access to the main database will be via a secure password-protected web-interface (NHS clinical portal). Surgical data will be entered on the NHS network via a generic login to allow the surgical team to enter the data. No identifiable data will be visible and only data items necessary to enable linkage in the main database will be collected (NHS number, operation date and gender). Follow-up questionnaires will be submitted to the CTEU Bristol by post or the participant may choose to complete the questionnaire electronically. Participants will enter their data through a secure website of the University of Bristol; this is because participants cannot be provided with access to a database inside the NHS network.

Data will be entered promptly and data validation and cleaning will be carried out throughout the study. A study manual covering database use will be available and regularly maintained.

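### Phase B section 4.8 i calls confounding minor when each surgeon keeps to one technique, but its reason covers patient mix only and leaves confounding by operator open

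*Protocol*

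**What the plan says.** Phase B section 4.8 i describes two extremes of practice. In situation (a), surgeons "apply their preferred variant to all of their patients, irrespective of the patients' characteristics". For that case it states "we expect that the risk of bias due to confounding will not be a serious issue", and the reason given is "since all surgeons are likely to operate on a wide variety of patients". It adds that, if (a) can be shown, surgeon preference might serve as an instrumental variable. In situation (b), surgeons choose the variant patient by patient. Only there is confounding called potentially serious.

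Other parts of the document bear on this:

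- **Phase B section 8.1** says hazards will be estimated "after adjusting for important procedure, patient and surgeon confounding factors", in models that nest participants within surgeons within centres. It leaves the choice of model factors to the SAP.
- **Phase B section 5.7** says "we will consider the list of confounding factors in" Table 5. That table holds patient, disease, treatment and lifestyle items, and no surgeon item.
- **Phase B Table 1** records many steps of stoma formation. Neither it, nor Table 4, nor the data list in section 5.4 names the operator's grade, specialty or volume.
- **Phase A section 2** lists "the seniority of the surgeon performing the procedure" among possible influences on PSH. Phase A section 4.4 collects surgeons' years of training and sub-specialty, and Appendix I asks about specialist versus general and senior versus junior operators.
- **Phase B section 5.2** says stomas will be formed by each surgeon's habitual technique, so a pattern close to (a) is plausible.

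**The concern.** Similar patient mix across surgeons removes confounding by patient characteristics. It does nothing about differences between the surgeons. If technique is fixed within each surgeon, the comparison of mesh with no mesh, or of one trephine shape with another, is a comparison of the surgeons who prefer one with the surgeons who prefer the other. Skill, seniority, specialism, volume and the rest of the surgeon's routine go with the preferred variant. For operator confounding, (a) is therefore the harder case, although the plan presents it as the easier one.

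The instrument does not escape this. Under strict (a), preference and technique received are the same variable, so an instrumental analysis returns the crude between-surgeon contrast with the same bias. More generally, preference must be unrelated to PSH except through the step under study, and section 4.8 i does not consider that condition.

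Objectives 3 to 6 of Phase B, the technique comparisons, are at stake. A difference between groups of surgeons could be reported as the effect of a surgical step.

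**Working it through.** **1. Reproduce Table 3, used here only as a yardstick.** Inputs from Phase B section 4.7: N = 4000, two-sided 5%, incidence 40%.

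Detectable HR = exp[(z₀.₉₇₅ + z_power) / √(N × incidence × p(1−p) × (1−R²))]

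- 1:1, R² = 0, 90% power: exp[(1.960 + 1.282)/√(4000 × 0.4 × 0.25)] = exp(3.242/20) = 1.176. Table 3 gives 1.18.
- Same at 80% power: exp(2.802/20) = 1.150. Table 3 gives 1.15.
- All 60 cells agree to within about 0.005.

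**2. What a within-surgeon comparison can deliver.** If technique is constant within surgeon, its squared correlation with surgeon indicators is 1. Then 1−R² = 0 and no within-surgeon hazard ratio exists. Near that limit, the detectable HR (1:1, 40%, 90% power) rises from 1.26 at R² = 0.5, the largest value in Table 3, to 1.67 at 0.9 and 2.06 at 0.95. Under (a) the estimate must come from between surgeons.

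**3. Size of between-surgeon bias with no true effect.** Let σ be the SD of the surgeon effect on log hazard and ρ its correlation with technique. The regression of surgeon effect on technique gives

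spurious log HR ≈ ρσ / √(p(1−p))

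The documents give neither σ nor ρ; both ranges are assumptions. At 1:1 the divisor is 0.5:

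| | σ = 0.2 | σ = 0.3 | σ = 0.4 |
|---|---|---|---|
| ρ = 0.2 | exp(0.08) = 1.083 | exp(0.12) = 1.127 | exp(0.16) = 1.174 |
| ρ = 0.3 | exp(0.12) = 1.127 | exp(0.18) = 1.197 | exp(0.24) = 1.271 |

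Two of the six cells exceed 1.18. At ρ = 0.2 none does.

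For rarer variants the same grid gives 1.11 to 1.38 at 1:5 (Table 3: 1.24) and 1.15 to 1.52 at 1:10 (Table 3: 1.33). These deserve less weight. Holding ρ = 0.3 fixed widens the implied gap between technique groups from 0.3/0.5 = 0.60 surgeon SDs at 1:1 to 0.3/0.2875 = 1.04 at 1:10.

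**4. Does nesting remove it?** Take an unmeasured binary surgeon factor with hazard ratio 1.5, present in 70% of one technique group and 30% of the other (assumed). Approximate spurious HR = (1 + 0.5 × 0.7)/(1 + 0.5 × 0.3) = 1.35/1.15 = 1.17. At 60% v 40% it is 1.08; at 80% v 20% it is 1.27.

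A simulation of the 70% v 30% case used 280 surgeons with 14 patients each (assumed), technique fixed within surgeon, true HR 1.00 and 100 runs:

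| Cox model, surgeon-clustered standard errors | HR | Null rejected |
|---|---|---|
| Surgeon factor omitted | 1.18 | 79% |
| Surgeon factor included | 1.00 | 5% |

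A linear model for the event with a surgeon random intercept (30 runs) showed the same pattern: risk difference 0.046 without the factor, −0.001 with it. Modelling the clustering does not remove the bias; measuring the factor and adjusting for it does.

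**The case against.** The strongest reply is that section 8.1 already commits to adjusting for procedure, patient and surgeon factors without limiting this to situation (b), and leaves the covariate list to the SAP. Section 4.8 i presents (a) and (b) as extremes and the instrument only as a possibility, and section 5.7 expects confounding to be handled in some way. This largely stands, and it rules out several stronger readings:

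- **That under (a) the plan will leave technique contrasts unadjusted.** Section 8.1 says otherwise.
- **That bundled steps are unmeasured.** Table 1 records incision size and shape, deep-layer closure and mesh fixation, and section 8.1 promises adjustment for procedure factors.
- **That surgeon identity is not captured.** A reader might infer this from "Surgical data will be entered on the NHS network via a generic login" in section 13.2.1 and the three linkage items named there. Those items link patient records and do not define the e-CRF. The e-CRF is completed with reference to the lead surgeon (section 4.8 iii), and the hierarchical model needs surgeon identity.
- **That surgeon preference is an invalid instrument outright.** Its validity is conditional and can partly be checked against Table 1 data.
- **That technique cannot be separated from operator at all.** This is exact within a surgeon. Across many surgeons comparison is possible if operator traits are measured and adjusted for.
- **That harmful bias has been shown.** The inputs are assumed, and the yardsticks are Table 3's smallest 90%-power values for each ratio.

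Three things survive the reply. The reasoning for (a) in section 4.8 i is incomplete whatever the SAP says. An SAP cannot adjust for operator traits that were not collected. The nesting promised in section 8.1 does not do that job.

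**Conclusion.** The point holds in this form: the conclusion for situation (a) rests on patient mix alone and does not follow, because operator characteristics and bundled steps can still confound technique contrasts and can invalidate the instrument. Section 8.1 intends adjustment for surgeon factors, but Table 5 lists none and no Phase B data list names grade or specialty, although Phase A names seniority as a possible influence. The e-CRF may hold such items without the protocol saying so; in that case the gap is one of wording only.

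The size is illustrative. At 1:1 use the assumed range gives a spurious hazard ratio of 1.08 to 1.27 against a detectable 1.18, reached only in the upper part of the range. The result depends on assumed σ, ρ, factor imbalance and cluster sizes, none of which the documents supply. The correction should be made because it is cheap and protects the main technique comparisons.

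**What to change.** 1. **Section 4.8 i.** Reword situation (a) to say that consistent surgeon preference limits confounding by patient mix but leaves confounding by operator and by bundled steps, and refer to the adjustment in section 8.1.
2. **Instrument.** Allow surgeon preference as an instrument only if balance is shown across preference groups in operator characteristics and in the other Table 1 steps.
3. **Data items and Table 5.** Add grade and specialty (colorectal or general) of the person forming the stoma to the e-CRF, or name them in the protocol if already there. Add both to Table 5, with study stoma volume derived from surgeon identity, so that Table 5 matches section 8.1.
4. **Reporting.** Where surgeons use more than one variant, report the within-surgeon estimate, adjusted for patient factors because choice by patient then matters. Label between-surgeon estimates as such.

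**Cost.** A few e-CRF items and revised wording. Grade and specialty for cases already entered would have to be recovered from site records, and the documents do not say whether those hold them. Within-surgeon estimates will have wider intervals, as step 2 of the working shows, and cannot be obtained for surgeons who never vary.

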#### *ii.* Bias in selection of participants into the study (selection bias)

Bias in selection of participants cannot affect the cohort study because we will study an inception cohort from the date of index surgery, carefully applying the eligibility criteria for the study without selection.

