## 4.2 Study design

This is a multi-centre, pragmatic cohort study to follow-up participants from the date of index stoma formation surgery. Follow-up will continue for a minimum of 2 years post-operatively, until closure of the cohort or death.

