## Table 1.

## Table 1:Key surgical steps of interest

1. Trephine Formation
Subcutaneous tissue excised
Relationship of the muscle layer incision to the rectus abdominis
Anterior sheath: was a laparoscopic trocar used to puncture the anterior sheath
Size of incision [widest diameter in mm]
Shape of incision
Was any of the anterior sheath removed
Adjustments made to the size of the incision
Sutures used to buttress end of incision
Posterior sheath: was a laparoscopic trocar used to puncture the anterior sheath
Size of incision [widest diameter in mm]
Shape of incision
Was any of the posterior sheath removed
Adjustments made to the size of the incision
Sutures used to buttress end of incision
Muscle fibres separated with blunt dissection
Intra-operative vessel damage - epigastric vessel
Location of trephine in relation to port site (Laparoscopic procedures only)
Reinforcing the Stoma Trephine with Mesh
2. Reinforcing the Stoma Trephine with Mesh
Was mesh used to reinforce stoma trephine
Mesh product code
Mesh cut or adjusted
Diameter of mesh inserted if changed from original [in mm]
Shape of mesh inserted if changed from original
Location of mesh placement
Route used to position mesh
What shape was the keyhole
What size was the keyhole [in mm]
Mesh secured to abdominal wall (including sheath, muscle, peritoneum)
Mesh secured to stoma serosa
3. Use of the Stoma as a Specimen Extraction Site
Stoma trephine used as an extraction site
4. Closure of other Wounds Formed during the Procedure
Main abdominal incision
Biggost post site [in mm]

Closure of deep layer

5. Spouting the Stoma Lumen

Has the stoma been spouted

Participants' characteristics at baseline will be documented, consistent with the variables agreed as potentially prognostic for PSH in the Phase A consensus process when identifying important surgical variations.

SCNs will also document common complications that arise in hospital before discharge (**Table 2**). Complications can be both prognostic for PSH and a secondary outcome (see 4.6.2) reflecting short-term risks.

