## 5. Study methods

## 5.1 Participant recruitment

The care of patients undergoing large and small bowel elective surgery for cancer or for inflammatory bowel disease is co-ordinated in all centres by specialist multi-disciplinary teams (MDTs). The MDTs meet regularly and consider all patients on the basis of their relevant staging investigations and other assessments. As part of usual care, a SCN or a surgeon will meet a patient identified by the MDT as requiring resection and stoma formation before surgery. The SCN or surgeon will give information about the study (patient information leaflet, PIL) to potential participants. Patients will be given as long as possible to consider the study before being approached for consent (at least 24 hours for elective surgery and usually more than 24 hours for expedited surgery). On rare occasions when a theatre becomes unexpectedly available, patients undergoing expedited surgery may be asked for consent less than 24 hours after receiving information about the study. SCNs approaching patients will not consent a patient if he/she requests longer thinking time and this was not available; patients who are visibly distressed will not be approached for consent.

Patients may be consented retrospectively following their surgery, as well as prospectively. Retrospective consent will be sought from eligible patients when consent cannot be obtained preoperatively for example: when a final decision to form a stoma is not made until the patient is in theatre; and when there is not enough time to discuss or for patients to consider the study fully prior to surgery. Wherever possible, the patient will be informed about the study prior to their surgery.

We aim to recruit at least 70 NHS Trusts over a 12 month period. Participants will be recruited over 24 months. We anticipate that about 12000 patients will be screened during

this period, that 66% (n  $\approx$  8000) will be eligible and that 50% (n  $\approx$  4000) of eligible patients will consent to take part in the study. This equates to a recruitment rate of about 4 patients per centre / per month, although this average number will vary according to the workload of a centre. The proposed schema is shown in **Figure 1**.

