## Table 4:Timing and frequency of collection of data items

Footnotes:

\*In-patient and out-patient hospital episodes will be extracted from HES data, which will be requested periodically throughout the study.

Data collection will include the following elements:

- (a) A screening log of patients undergoing elective surgery to form a stoma. This log will be maintained by centres but data from the log will only be entered for eligible patients who consent to take part in the study (i.e. participants).
- (b) Confirmation of patient's eligibility against all eligibility criteria, written informed consent and patient's contact preferences (see below).
- (c) Baseline data characterising participants before surgery will be collected by the SCNs and obtained retrospectively from a HES data extract. Data from these sources will include any relevant diseases and comorbidities the participant may have and their current health status.
- (d) Surgery details will be collected by the surgical team in theatre and entered into an online database. These details will describe how the stoma is formed.
- (e) Details of a participant's recovery after surgery will be collected at discharge by the SCNs and obtained retrospectively from a HES data extract. These details will describe the patients post-operative stay including surgical or medical complications.
- (f) All follow up contacts between a participant and a SCN will be recorded by the SCNs; we also intend to obtain these details from local NHS stoma care databases used by hospitals when available.
- (g) Participants will be asked to complete health questionnaires, i.e. the EQ-5D-5L and SF-12, a purpose-designed questionnaire about stoma symptoms developed in Phase A [34], a questionnaire about how the participant is adapting to living with a stoma [43] and brief questions about primary care, social care and other resource use related to the stoma. Participants will be able to choose to receive the questionnaires by post or to complete them via an online secure website. Subject to their consent, we may also issue reminders to participants about completing questionnaires by text messaging.

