#### 11.4 Obtaining informed consent from participants

All participants will be given or sent a Patient Information Leaflet (PIL) and the opportunity to deliberate before being approached for their written informed consent. The majority of patients, those undergoing either elective or expedited (but not urgent or immediate) surgery to form a stoma, will meet with a SCN prior to surgery, who will describe the study

and address any concerns that the patients may have. In some instances, consent may be taken retrospectively following the participant's surgery. When this happens, participants will have the same opportunity to deliberate about participation before being approached for their written informed consent. If the patient declines the study, their intraoperative data will be deleted.

The member of the research team taking consent will be appropriately trained and delegated to perform their role. A copy of the signed Informed Consent form, along with a copy of the PIL will be given to the study participant to keep. Furthermore, the original signed informed consent form will be retained for trial records and a further copy will be placed in the patient's medical notes.

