## 16. Amendments to protocol

Amendment number (i.e. REC number)	Previous version	Previous date	New version	New date	Brief summary of change	Date of ethical approval (or NA if non- substantial)
SA 1	V1.0	11 October 2017	V2.0	05 November 2018	Change to eligibility criteria and addition of retrospective consent. Addition of health economic study objective.	07/12/2018

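### Section 4.8 rules out selection bias outright, but consent after surgery makes entry for that group depend on the early postoperative course

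*Protocol*

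**What the plan says.** Section 4.8 (ii) dismisses selection bias in absolute terms: "Bias in selection of participants cannot affect the cohort study because we will study an inception cohort from the date of index surgery". It adds that the eligibility criteria are applied without selection. Section 4.2 sets time zero accordingly, describing a "cohort study to follow-up participants from the date of index stoma formation surgery".

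Section 5.1 then says: "Patients may be consented retrospectively following their surgery, as well as prospectively". One trigger it gives is "when a final decision to form a stoma is not made until the patient is in theatre"; another is too little time before the operation. Section 11.4 repeats the provision: "In some instances, consent may be taken retrospectively following the participant's surgery". It also says that the intraoperative data of anyone who then declines are deleted. Neither section sets a latest time for retrospective consent. Section 16 records the source of the provision: "Change to eligibility criteria and addition of retrospective consent".

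Sections 4.4.1 and 4.4.2 require the patient to give written consent and exclude those without capacity. On the screening log, Section 5.4 item (a) says that "data from the log will only be entered for eligible patients who consent to take part in the study". On early complications, Section 4.5 says: "Complications can be both prognostic for PSH and a secondary outcome".

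**The concern.** The statement in Section 4.8 (ii) holds when consent precedes the operation. For a patient consented afterwards, time zero is surgery, but entry depends on being alive, having capacity and agreeing at some later time. That is selection on events after the exposure.

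Some of the protocol's own outcomes stand in the way of entry. Table 2 lists death, delirium, permanent stroke and ventilation or intensive care among the complications to be recorded. Death prevents retrospective consent; the others may delay or prevent it.

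The exposed quantities are:

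- the early secondary outcomes in Section 4.6.2: ICU stay, hospital stay, surgical site infection to 30 days and other complications;
- the index-admission cost, which Section 8.4 bases on length of stay;
- the QALYs, which combine survival with EQ-5D-5L from baseline onwards.

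A secondary route to the primary comparison exists because the protocol treats complications as potentially prognostic for parastomal hernia (PSH).

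**Working it through.** **Consistency of the text.** The conflict lies within the current text (Sections 4.2, 4.4, 4.8, 5.1 and 11.4). It does not rest on the amendment table, which only explains how it arose. Once entry may follow surgery and requires personal consent, a patient who dies first cannot enter. So selection can affect the cohort.

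**The plan's own figures.** The protocol gives no figure for this issue. Its only power figures are in Table 3 and do not depend on it. As a check, the 1:1, unadjusted, 40% row gives exp[(1.960 + 1.282)/√(4000 × 0.40 × 0.25)] = exp(3.242/20) = 1.18 at 90% power, as printed.

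**Inputs for an illustration**

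- Two-year mortality of about 15% (Section 5.10).
- Cohort of 4000 (Section 4.7).
- Retrospective share: not given; assumed 5% to 50%.
- Mortality before consent: not given. Low value from a constant hazard: −ln(0.85)/730 = 0.000223 per day, so 1 − exp(−0.000223 × 30) = 0.67% by day 30. Early hazard may be higher, so 3% is assumed as the high value.

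**Early mortality.** Let q be the true proportion dying before consent could be given, and f the share of would-be participants who can be approached only after surgery. The observed rate is q(1 − f)/(1 − qf).

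| q | f | Observed | Understatement (points) |
|---|---|---|---|
| 0.67% | 5% | 0.64% | 0.03 |
| 0.67% | 40% | 0.40% | 0.27 |
| 3% | 5% | 2.85% | 0.15 |
| 3% | 20% | 2.41% | 0.59 |
| 3% | 40% | 1.82% | 1.18 |

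The relative understatement is f(1 − q)/(1 − qf). For small q this is almost exactly f, so it only returns the assumed share.

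**Deaths that never enter.** With s the retrospective share of the 4000 enrolled, the number is 4000·s·q/(1 − q). For s = 5%, 10%, 25% and 50% this gives about 1, 3, 7 and 13 deaths at q = 0.67%, and about 6, 12, 31 and 62 at q = 3%.

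**Complications (all inputs assumed).** Take a true severe-complication rate of 20%, with such patients half as likely to consent afterwards. The retrospective group shows 0.20 × 0.5/(0.20 × 0.5 + 0.80) = 11.1%. The whole cohort shows (1 − s) × 20% + s × 11.1%, which is 19.6%, 19.1%, 17.8% and 15.6% for the four shares.

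**Comparison of techniques.** With no true effect and retrospective shares of 25% and 5% in two techniques, the complication risk ratio is 17.8/19.6 = 0.91. If such patients are 0.7 times as likely to consent, it is 18.7/19.7 = 0.95. With equal shares and equal early loss it is 1.

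**Primary outcome.** Section 4.6.1 requires symptoms as well as CT evidence, and Table 4 first schedules the stoma questionnaire at 6 months. Nobody becomes an incident case without reaching that questionnaire, whenever they consented.

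**The case against.** The best case for the plan is that the affected group may be small. Section 11.4 speaks of some instances and says that most patients meet a stoma care nurse beforehand; urgent and immediate surgery is excluded. Retrospective consent also admits patients whose stoma is decided in theatre, who would otherwise be missed. Sensitivity analyses belong largely to the statistical analysis plan, which is not at hand. All of this stands. It limits the size of the problem, but does not rescue a categorical denial.

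It also rules out several stronger readings that a reader might infer:

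- *Severe complications are certainly missed.* The documents do not say so. With no time limit, a patient with a long stay can still be approached after recovery. Only the exclusion of deaths before consent is certain.
- *Early event rates are understated by 20–40%.* That figure is the assumed share restated.
- *Retrospective participants have no preoperative EQ-5D-5L or SF-12.* Table 4 schedules these before surgery, and no section says what happens to them in retrospective cases.
- *Mesh cost-effectiveness is biased.* It is a between-group comparison, distorted only if retrospective consent or early loss differs by mesh use. Nothing in the protocol shows that it does.
- *The selection can never be examined.* Centres keep the screening log, and aggregate counts are not precluded. But only consenters' log data are planned for entry, and a later analysis plan cannot recover counts that were not collected.

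**Conclusion.** The point holds in a limited form. The claim in Section 4.8 (ii) is wrong as written for retrospectively consented participants: entry depends on surviving and being able to consent after the exposure, while the clock starts at surgery. Descriptive levels of early outcomes, and the cost and QALY inputs, can look too favourable. Comparisons of techniques are affected only if retrospective consent or early loss differs by technique.

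The size cannot be derived from the protocol. The range of about 0.03 to 1.2 percentage points for early mortality rests on assumed shares of 5% to 40% and early mortality of 0.67% to 3%. The complication figures rest on further assumptions. The PSH endpoint is largely protected, leaving only the indirect route through prognostic complications. This is worth correcting because it is cheap and partly irrecoverable later, but it does not undermine the primary analysis.

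**What to change.** 1. In Section 4.8 (ii), replace the absolute statement with an acknowledged risk for participants consented after surgery, naming the early outcomes concerned.
2. Record the consent date and whether consent came before or after surgery. Operation date is already collected (Section 13.2.1).
3. Collect anonymised aggregate counts from the centre logs of eligible patients not enrolled, by timing (before or after surgery) and reason (died, lost capacity, declined, not approached).
4. Name a sensitivity analysis restricted to prospectively consented participants for the early outcomes, QALYs and the primary comparison, in the protocol or the statistical analysis plan.

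The cost is a wording change, one date with a derived flag, a short aggregate return from centres and one extra analysis. Care and sample size do not change. The restricted analysis will have wider intervals and will omit patients whose stoma was decided in theatre. That changes the target population, so it should accompany the main analysis and not replace it. Delayed entry at consent would add little for PSH, given the 6-month start of symptom collection.
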